## 2.1 Primary estimands

The primary clinical question of interest is: Does [F]CTT1057 target PSMA expressing PCa cells, allowing to obtain adequate [F]CTT1057 PET/CT images to detect and localize PSMA positivity using histopathology as SoT?

The justification for the primary estimand is that we wish to assess the diagnostic performance of [F]CTT1057 PET in detecting and localizing PSMA positivity. For this reason, newly-diagnosed high risk PCa patients will undergo a [F]CTT1057 PET/CT scan within 6 weeks before surgery (but not sooner than 48 hours after the completion of the [F]CTT1057 PET/CT scan), and results of the [F]CTT1057 PET/CT scans will be compared against the histopathology results (SoT) in the dissected tissue specimens (primary tumor and PLN), both at a patient and region level.

The primary estimands are described by the following attributes:

Primary estimand 1:

- Population: Untreated high risk PCa patients according to D'Amico classification (Stage  $\geq$  T2c or PSA level  $>20$ ng/ml or Gleason score  $\geq 8$ ) (D'Amico et al 1998), who are scheduled or planned RP and lymph node resection. Further details about the population are provided in Section 5.
- Variables: Proportion of patients that test positive on both [F]CTT1057 and SoT (TP) among those that are SoT positive ( TP + FN), considering PSMA positive patients are those who show at least one pathological [F]CTT1057 uptake either in the primary tumor and/or metastatic PLN, with anatomically localized correspondence with the SoT.

3. Treatment (investigational imaging agent) of interest: [F]CTT1057 injected as a single intravenous dose of approximately 370 MBq and subsequent PET/CT scan. Further details about the investigational imaging agent are provided in [Section 6](#).
4. Handling of remaining intercurrent events:
  - Patients who received the investigational imaging agent [F]CTT1057 but did not undergo/complete the PET/CT scan for any reasons (e.g. consent withdrawal, PET camera failures, etc.), will be excluded from the primary analysis. Details on how to handle intercurrent events are provided in [Section 12.4.3](#).

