A central read of the PET/CT scan will be performed at a Contract Research Organization (CRO) by a total of three independent nuclear medicine physicians or radiologists experienced in reading oncology PET, who will be blinded to patient data, including the clinical condition of the patient, results of histopathology/biopsy, and results of conventional imaging. Patients and regions will be graded on a two-point scale by each reader (0 = negative; 1 = positive). The results from each of the 3 readers will be individually compared to the SoT to generate per-reader performance. An individual PET reader will be considered successful if he/she meets predefined thresholds for both co-primary endpoints, and at least two of three readers should be successful for overall study positive. PET results will be compared to histopathology results, and anatomically localized positive lesions in both PET and histopathology will be considered “TP” for sensitivity and specificity calculations as the primary endpoints of the study.

[figure not shown]
Regions defined for this study are prostate region (comprising prostate bed/prostate gland and any local invasion of the urinary bladder, rectum or seminal vesicles), PLN region, extra-PLN region, skeletal region and visceral region.

The criteria to be applied for PET positivity is the following:

- A patient will be judged as positive if at least one lesion in any region is visually positive.
- A region will be judged as positive if at least one lesion in the region is visually positive.
- Visually PET positive lymph nodes will be considered greater than blood pool (adjacent or mediastinal blood pool).
- PET positive bone lesions will be considered greater than physiologic bone marrow.
- PET positive prostate, prostate bed and visceral lesions will be considered greater than physiologic background activity of the involvement organ or anatomic site, as previously described (Ceci et al 2015, Eiber et al 2015, Fendler et al 2019).

Only prostate region and PLN will be used as regions for comparison to the SoT and co-primary endpoint calculations.

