### 12.4.1 Definition of primary endpoint(s)/estimand(s)

The co-primary endpoints of the study are patient-level sensitivity and region-level specificity.

- Patient-level sensitivity is defined as the proportion of PSMA TP patients among PSMA TP patients and PSMA FN patients.
  - PSMA TP patients are those who show at least one pathological [F]CTT1057 uptake either in the primary tumor and/or metastatic PLNs with anatomically localized correspondence with the SoT.
  - PSMA FN patients are those who do not show any pathological [F]CTT1057 uptake either in the primary tumor or metastatic PLNs but will be confirmed having primary tumor or metastatic PLNs with the SoT.
- Region-level specificity is defined as the proportion of PSMA TN PLN regions among PSMA TN PLN regions and PSMA FP PLN regions.
  - PSMA TN PLN regions are regions that test negative for PLN on [F]CTT1057 and confirmed negative on the SoT.
  - PSMA FP PLN regions are regions that test positive for PLN on [F]CTT1057 but verified negative on the SoT.

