A large variability in sensitivity of PSMA-PET in the primary staging setting has been reported. Two recent systematic reviews of [Ga]PSMA PET /CT diagnostic accuracy focused on the PS population using pathology as SoT, sensitivity of 33–99% across studies has been reported (Corfield et al 2018), as well as pooled sensitivity and specificity ranges of 23-100% and 67-100% respectively (Petersen and Zacho 2020). Recent preliminary data on the diagnostic efficacy of F-18-rhPSMA-7.3 PET imaging in PS patients compared to histopathology (n=56) reported a 95% CI low bound patient level sensitivity of 54.4% (81.3 (95% CI-54.4-96.0) (Maurer et al 2020). CT and MRI are the standard of care imaging procedures for measuring tumors at baseline and lesions selected for response assessment as per RECIST criteria 1.1 (Eisenhauer et al 2009). A meta-analysis on the diagnostic accuracy of CT and MRI in the staging of pelvic lymph nodes in patients with PCa reported a pooled sensitivity of 0.42 (95% CI 0.26-0.56) for CT, and of 0.39 (95% CI 0.22-0.56) for MRI (Hövels et al 2008). A study evaluating the diagnostic value of [Ga]PSMA PET versus CT and MRI for lymph node staging in 130 consecutive patients who got RP and PLN dissection after PET/Magnetic Resonance (MR) (n=95) and PET/CT (n=35) and who had tumor specimens available for reanalysis to correlate with PET reported a sensitivity of 43.9% (95% CI 28.5-60.3) and 85.4% specificity (95% CI 76.3-92.0) for morphological imaging alone (CT and MRI) (Maurer et al 2016).

Taking all the above into consideration, an overall patient-level sensitivity of 50% and a region level specificity of 70% will be considered as unacceptably low. Hence, the sample size calculation will be performed based on the null and alternative hypotheses as follows.

- Patient-level sensitivity

For patient-level sensitivity, the null hypothesis H0: patient-level sensitivity p0 = 0.50 will be tested against the alternative hypothesis H1: p1>0.50, assuming a sensitivity of 0.63 under the alternative hypothesis, approximately 156 patients with primary tumor and/or metastatic lymph nodes would achieve 90% statistical power to detect a change in sensitivity of 0.13 using a one-sided binomial test at a target significance level of 2.5%. Taking into account 20% dropout rate, 195 patients can ensure the 90% statistical power.

- Region-level specificity

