#### 1.2.1 **Primary estimand(s)**

The primary clinical question of interest is: Does [F]CTT1057 target PSMA expressing PCa cells, allowing to obtain adequate [F]CTT1057 PET/CT images to detect and localize PSMA positivity using histopathology as SoT?

The justification for the primary estimand is that we wish to assess the diagnostic performance of [ $^{18}$ F]CTT1057 PET in detecting and localizing PSMA positivity. For this reason, newly-diagnosed high risk PCa patients will undergo a [ $^{18}$ F]CTT1057 PET/CT scan within 6 weeks before surgery (but not sooner than 48 hours after the completion of the [ $^{18}$ F]CTT1057 PET/CT scan), and results of the [ $^{18}$ F]CTT1057 PET/CT scans will be compared against the

Novartis	Confidential	Page 13 of 43
SAP Amendment 2		Study No. CAAA405A12302

histopathology results (SoT) in the dissected tissue specimens (primary tumor and PLNs), both at a patient and region level.

The co-primary estimands are described by the following attributes:

Primary estimand 1:

- Population: Untreated high risk PCa patients according to D'Amico classification (Stage ≥ T2c or PSA level >20ng/ml or Gleason score ≥8) (D'Amico et al 1998), who are scheduled or planned RP and lymph node resection. Further details about the population are provided in Section 5 of the protocol.
- 2. Variable: Patient level sensitivity, defined as the proportion of participants that test positive on both [F]CTT1057 and SoT (TP) among those that are SoT positive (TP + FN), considering PSMA positive participants are those who show at least one pathological [F]CTT1057 uptake either in the primary tumor and/or metastatic PLN, with anatomically localized correspondence with the SoT.
- 3. Treatment (investigational imaging agent) of interest: [F]CTT1057 injected as a single intravenous dose of approximately 370 MBq and subsequent PET/CT scan. Further details about the investigational imaging agent are provided in Section 6 of the protocol.
- 4. Intercurrent events:
  - Participants who received the investigational imaging agent [F]CTT1057 but did not undergo/complete the PET/CT scan for any reasons (e.g. consent withdrawal, PET camera failures, etc.). Details on how to handle intercurrent events are provided in Section 2.5.3.

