#### 2.5.1 **Primary endpoint(s)**

The co-primary endpoints evaluated for participants in the EFF are the following:

**Patient-level Sensitivity** of  $[^{18}F]CTT1057$  PET imaging, defined as the proportion of participants that test positive on both  $[^{18}F]CTT1057$  and SoT (TP) among those that are SoT

Novartis
SAP Amendment 2

positive (TP + FN), considering PSMA positive participants are those who show at least one pathological [ $^{18}$ F]CTT1057 uptake either in the primary tumor (prostate region) and/or metastatic PLN region, with anatomically localized correspondence with the SoT. See Section 1.2.1 for Primary Estimand.

**Region-level Specificity** of [18F]CTT1057 PET imaging, defined as the proportion of PLN regions that test negative on both [ $^{18}$ F]CTT1057 and SoT (TN) among those PLN regions that test negative on the SoT (TN + FP), considering PSMA negative PLN regions are those which do not show any pathological [18F]CTT1057 uptake within the region. See Section 1.2.1 for Primary Estimand.

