## 2.6.1 Secondary endpoint(s)

Secondary endpoints are defined for the EFF unless otherwise specified with details given as follows:

**Patient-level specificity** is defined as the proportion of TN participants among those who are TN or FP.

**Patient-level positive predictive value** is defined as the proportion of TP participants among those who are TP or FP.

**Patient-level negative predictive value** is defined as the proportion of TN participants among those who are TN or FN.

**Patient-level accuracy** is defined as the proportion of TP and TN participants among all participants in EFF (regardless of TP, TN, FP, FN)

where TP, TN, FP, FN participants are defined as follows:

- PSMA TP participants are those who show at least one pathological [F]CTT1057 uptake either in the primary tumor and/or metastatic PLNs with anatomically localized correspondence with the SoT, regardless of co-existing FP lesions in those two regions.
- PSMA TN participants are those who do not show any pathological [F]CTT1057 uptake neither in the primary tumor nor metastatic PLNs and will be confirmed NOT having primary tumor nor metastatic PLNs with the SoT.
- PSMA FP participants are those who are not TP and show at least one pathological [F]CTT1057 uptake either in the primary tumor and/or metastatic PLNs but will be verified NOT having primary tumor nor metastatic PLNs with the SoT or none of the lesions is correctly localized in anatomical location by the SoT.
- PSMA FN participants are those who do not show any pathological [F]CTT1057 uptake neither in the primary tumor nor metastatic PLNs but will be confirmed having primary tumor or metastatic PLNs with the SoT.

Number of TP, TN, FP, FN participants will be presented and used to calculate the diagnostic performance parameters.

Two-sided exact binomial 95% CIs for diagnostic performance parameters will be calculated.

**Region-level sensitivity** is defined as the proportion of TP PLN regions among those that are TP or FN.

**Region-level sensitivity** will also be presented, excluding PLNs showing metastasis < 2 mm (micro-metastasis).

**Region-level positive predictive value** is defined as the proportion of TP PLN regions among those that are TP or FP.

Novartis	Confidential	Page 24 of 43
SAP Amendment 2		Study No. CAAA405A12302

**Region-level negative predictive value** is defined as the proportion of TN PLN regions among those that are TN or FN.

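### Co-primary patient-level sensitivity has two conflicting denominators: all SoT-positive participants, or TP + FN, which leaves out SoT-positive participants whose only uptake is mislocalised

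*SAP*

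**What the plan says.** Two descriptions of the denominator are in force.

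- **All SoT-positive participants.** Protocol 2.1 takes the proportion "among those that are SoT positive ( TP + FN"). SAP 1.2.1 repeats this, "among those that are SoT positive (TP + FN"), and SAP 2.5.1 does the same: "positive (TP + FN), considering PSMA positive participants are those". Each treats SoT positive and TP + FN as one group.
- **The TP and FN cells only.** Protocol 12.4.1, the primary-endpoint section, states: "Patient-level sensitivity is defined as the proportion of PSMA TP patients among PSMA TP patients and PSMA FN patients".

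The cells are defined as follows.

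- **TP** requires uptake that corresponds anatomically with the SoT (protocol 12.4.1, SAP 2.6.1). Protocol 4.1 agrees: "anatomically localized positive lesions in both PET and histopathology will be considered" TP. The match is judged on prostate sextants and left/right nodal sides (protocol 3 and 16.3).
- **FN** requires a positive SoT and no uptake: "PSMA FN patients are those who do not show any pathological" uptake (protocol 12.4.1; same rule in protocol 12.5.1 and SAP 2.6.1).
- **FP** covers uptake in a participant shown to have no tumor, "or none of the lesions is correctly localized in anatomical location by the SoT" (SAP 2.6.1; same clause in protocol 12.5.1).

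A reader meets the first co-primary criterion if the lower limit of the exact 95% CI exceeds 0.50. The study needs two of three readers to meet both co-primary criteria (SAP 2.5.2).

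**The concern.** Take a participant with cancer at surgery whose only PET uptake lies in a sextant or nodal side that does not match pathology. He is not TP, because nothing is correctly localised. He is not FN, because uptake is present. He is not TN, because the SoT is positive. The definitions make him FP. The first part of the FP definition already covers SoT-negative participants, so the localisation clause exists to add SoT-positive ones. He is thus SoT positive but outside TP + FN.

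A programmer following SAP 2.5.1 would keep him as a miss. One following protocol 12.4.1 and the SAP 2.6.1 cells would drop him. Neither document says which expression governs.

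The choice is not neutral: removing misses from the denominator can only raise the estimate, and this is a co-primary with a pass/fail threshold. If it is made after the counts are known, that endpoint is no longer prespecified.

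**Working it through.** **Inputs.** From protocol 12.8.1 and SAP 3.1: null sensitivity 0.50, alternative 0.63, one-sided 2.5%, 90% power, 156 patients, 20% dropout. From SAP 2.5.2 and 5.4.1: two-sided exact (Clopper-Pearson) 95% CI, success if the lower limit exceeds 0.50. The mislocalised-only share m of SoT-positive participants is not in the documents. I take 0% to 10% as an assumed range.

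**1. The plan's own figure.** For n = 156 the smallest passing count is 91 TP. P(X ≥ 91) is 2.25% at 0.50 and 90.1% at 0.63, and 156 is the smallest n reaching 90% power. Then 156/0.8 = 195. The stated 156 and 195 reproduce, with every one of the 156 in the denominator.

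**2. Same data, two denominators.** The lower limit for x successes in n is the 2.5% quantile of Beta(x, n − x + 1). Take 156 SoT-positive participants and drop k mislocalised ones, where k is the smallest number that turns a fail into a pass:

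| TP | TP/156 | Lower limit | k | TP/(TP + FN) | Lower limit |
|---|---|---|---|---|---|
| 90 | 57.7% | 0.4954, fail | 2 | 90/154 = 58.4% | 0.5023, pass |
| 89 | 57.1% | 0.4889, fail | 4 | 89/152 = 58.6% | 0.5029, pass |
| 88 | 56.4% | 0.4825, fail | 6 | 88/150 = 58.7% | 0.5035, pass |
| 87 | 55.8% | 0.4761, fail | 7 | 87/149 = 58.4% | 0.5004, pass |
| 85 | 54.5% | 0.4633, fail | 11 | 85/145 = 58.6% | 0.5015, pass |

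**3. Chance of passing.** Let t be the true share of SoT-positive participants who are TP. Under TP + FN, the number dropped is K ~ Bin(156, m), and TP given K is Bin(156 − K, t/(1 − m)). The estimate is therefore inflated by 1/(1 − m). Summing exactly over K, for one reader and the sensitivity criterion alone:

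| m | t = 0.50 | t = 0.63 |
|---|---|---|
| 0% | 2.25% | 90.1% |
| 2% | 3.5% | 93.7% |
| 5% | 8.1% | 97.8% |
| 10% | 23.4% | 99.8% |

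With all SoT-positive participants in the denominator, the figures stay at 2.25% and 90.1% whatever m is.

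**4. Two of three readers.** If the readers agree perfectly, the t = 0.50 column applies unchanged. If they are independent, 3p²(1 − p) + p³ gives 0.15%, 0.37%, 1.9% and 13.9% at m = 0%, 2%, 5% and 10%. Specificity is not modelled.

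**5. If 0.63 was meant as TP/(TP + FN).** The share among all SoT-positive participants is then 0.63(1 − m). At m = 2%, 5% and 10%, per-reader power with the SoT-positive denominator is 83.1%, 68.2% and 37.2%, against 88.4%, 87.9% and 85.9% with TP + FN. Which meaning 0.63 carries therefore matters to the design too.

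**The case against.** The strongest reply is that no rival formula exists: every co-primary statement writes TP + FN. SAP 1.2.1 and 2.5.1 also name SoT-positive participants as the denominator and require localised correspondence for PSMA positivity. On that reading a mislocalised-only participant is a miss inside the denominator, and the contrary FP clause appears only among the secondary endpoints. This is a sensible reading and probably the better one, but the text does not make it control. Protocol 12.4.1 is the primary-endpoint section, and its FN definition excludes him without help from the FP clause. Nor can uptake in the primary tumor be read as uptake in the true lesion, which would make him FN: the FP definition uses the same phrase for participants with no tumor, and SAP 2.5.1 glosses it as the prostate region.

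On sample size, protocol 12.8.1 literally counts SoT-positive patients: "approximately 156 patients with primary tumor and/or metastatic lymph nodes would achieve 90% statistical power". But protocol 12.8 and SAP 3 describe the 156 as evaluable participants, so the number supports the SoT-positive reading without proving intent.

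Other points stand as limits. The share m is unknown and may be zero. One matching lesion makes a participant TP whatever else is seen, which keeps m down. Matching rules may be in the imaging charter or in redacted text. At m = 1% the per-reader rate at 0.50 is only 2.7%, and at a true sensitivity of 0.70 a reader passes at least 99.9% of the time either way. The four counts and accuracy are reported, so the loss would be visible, but they do not decide success.

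**Conclusion.** The concern holds. SoT positive and TP + FN are presented as the same group, and the plan's own cell definitions make them different. Applying protocol 12.4.1 as written removes mislocalised-only participants and inflates sensitivity by 1/(1 − m).

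The practical effect is concentrated near the threshold, where two mislocalised participants out of 156 can turn a failing reader into a passing one. At the null value the nominal 2.5% level is exceeded under each assumed share from 2% upward. At the design value of 0.63 the criterion is usually met under either denominator. These figures assume 156 SoT-positive participants and a constant m, and they cover the sensitivity criterion alone. Study success also needs specificity and two readers.

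This must be fixed because one prespecified co-primary currently permits two computations that can give opposite results.

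**What to change.** In SAP 2.5.1 and protocol 12.4.1, define co-primary patient-level sensitivity as TP divided by all SoT-positive participants in the EFF, with SoT-positive participants who have only mislocalised uptake counted as misses. Align protocol 2.1 and 12.5.1 and SAP 1.2.1 and 2.6.1. Either delete the equation with TP + FN, or add a separate cell for SoT-positive mislocalised participants and include it in the denominator. Report the number in that cell for each reader.

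Two consequences should be stated. PPV and NPV keep all PET-positive and all PET-negative participants as denominators. SoT-positive mislocalised participants should leave the patient-level specificity denominator, which they now enter through FP.

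The cost is a few sentences before database lock and no new data. The SAP change can be made first and recorded in SAP section 4. A protocol edit needs a written amendment and the approvals in protocol 14.1, but the analysis rule need not wait for it. The downside is that reported sensitivity will be lower than TP/(TP + FN) by a factor of 1 − m, and power falls below 90% if 0.63 was meant on the TP + FN basis. The sponsor should state which basis was used.

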#### Characterize the safety and tolerability of [18F]CTT1057

Further discussion of the safety and tolerability endpoints to support the secondary objective analysis is included in Section 2.8.

#### Pharmacokinetics in humans in subset of approximately 10 patients

Further discussion of the pharmacokinetics analysis is included in Section 2.9.

#### 2.6.2 Statistical hypothesis, model, and method of analysis

Patient-level diagnostic performance parameters include:

- Patient-level specificity
- Patient-level positive predictive value •
- Patient-level negative predictive value
- Patient-level accuracy
- Detection rate of distant metastasis evaluated for all other regions (i.e. extra PLN, • skeletal and visceral)

See details given in Section 2.6.1.

Region-level diagnostic performance parameters include:

- Region-level sensitivity including and excluding micro-metastasis
- Region-level positive predictive value
- Region-level negative predictive value •
- Region-level accuracy •

See details given in Section 2.6.1.

[F]CTT1057 scan inter-reader variability will be assessed by Fleiss' Kappa ( $\kappa_1$ ) statistic (Fleiss 1971) defined below:

$$\kappa_1 = \frac{\overline{P} - \overline{P}_e}{1 - \overline{P}_e}.$$

Let N represent the total number of participants who have evaluable PET/CT, n the number of central readings per participant n = 3 ( $\overline{OB}$ ), and k = 2 the number of outcome categories ( $\overline{OB}$ ) into which assignments are made. Participants  $i = 1, ..., Nby j = 1, ..., k^{(OB)} n_{ij}^{(OB)}$  represent the number of readers who assigned the *mj* participant to the *j*th category. Then

$$P_{i} = \frac{1}{n(n-1)} \sum_{j=1}^{k} n_{ij} (n_{ij} - 1) \text{ and } \bar{P} = \frac{1}{N} \sum_{i=1}^{N} P_{i};$$
$$p_{j} = \frac{1}{Nn} \sum_{i=1}^{N} n_{ij} \text{ and } \bar{P}_{e} = \sum_{j=1}^{k} p_{j}^{2}.$$

A contingency table of N row (N is the number of participants who have evaluable PET/CT) by 2 (the number of outcome categories) will summarize the frequency of agreements among the 3 readers for each case and each patient-level outcome (i.e. positive, negative). The counts across each of the *N* rows will sum up to 3 (number of readers).

Based on the contingency table as described above, a Fleiss's Kappa statistic and corresponding 95% confidence interval will be estimated based on asymptotic estimation of the standard error (i.e.

$$\widehat{se}(\kappa_1) = \frac{\sqrt{2}}{\sum_{j=1}^k p_j (1-p_j) \sqrt{Nn(n-1)}} \sqrt{\left(\sum_{j=1}^k p_j (1-p_j)\right)^2 - \sum_{j=1}^k p_j (1-p_j)(1-2p_j)} \quad \text{(Fleiss,}$$
New Landis 1979: Eleiss L Levin B. Paik MC 2003) and the normality assumption (i.e. 95% CL

Nee, Landis 1979; Fleiss J, Levin B, Paik MC 2003) and the normality assumption (i.e. 95% CI

Novartis	Confidential	Page 26 of 43
SAP Amendment 2		Study No. CAAA405A12302

can be calculated as:  $\kappa_1 \pm 1.96 \hat{se}(\kappa_1)$ ). An additional table will be presented to show the distribution of agreements with the number (%) of scans agreed by two readers and the number (%) of scans agreed by all three readers. Inter-reader variability will be calculated for the SAF.

[F]CTT1057 scan intra-reader variability will be assessed by Cohen's Kappa ( $\kappa_2$ ) statistic. To assess the intra-reader variability, each of the three readers will re-read the same 20 randomly selected cases (with evaluable PET/CT) but each case will be presented to each reader in a random order. The readers will not reference any previous read results nor discuss any of these cases at any time during the read process. Each reader will use the same method to read the randomly presented cases as they did in the previous reads. Intra-reader agreement will first be evaluated separately for each of the 3 readers using Cohen's kappa statistic ( $\kappa_2$ ) as described below:

**Step 1:** A 2 by 2 contingency table (e.g. Table 2-2) will be calculated to summarize the frequency of concordance and discordance for patient-level positivity or negativity. The counts in the table will add up to 20 in total (i.e. a + b + c + d = 20).

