A Phase-I study in 20 PCa patients (n=5 primary staging, n=15 metastatic-castration resistant prostate cancer (mCRPC)) (Behr et al 2019) has shown an acceptable safety profile, without any radiotracer-related adverse reactions. The biodistribution of [F]CTT1057 in humans is similar to that of other PSMA-targeted agents, and exposure rates of [F]CTT1057 are also similar to those of the urea-based PET compounds, with the advantageous exception of lower exposure to kidneys and salivary glands. Preliminary evidence of diagnostic performance of [F]CTT1057 PET in detecting and localizing PSMA-positive tumors was provided from the n=5 primary staging patients using pathology as SoT. Abnormal [F]CTT1057 PET uptake corresponding to the pathology-proven cancer was shown in 4 of the 5 subjects. The only subject who did not show PET uptake in the primary tumor had the lowest PSA in the cohort. The Phase-I study also demonstrated that metastatic lesions are detected with higher sensitivity on [F]CTT1057 imaging than on conventional imaging (Behr et al 2019). Another smaller study showed that the image quality on [F]CTT1057 PET imaging was qualitatively similar to that obtained on [Ga]Ga-PSMA-11 PET (Behr et al 2017).

Further details on [F]CTT1057 can be found in the Investigator's Brochure (IB).

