## 5.1 Inclusion criteria

Participants eligible for inclusion in this study must meet **all** of the following criteria:

- 1a. Untreated high risk biopsy-proven PCa patients according to D'Amico classification (Stage  $\geq$  T2c or PSA level  $>20$ ng/ml or Gleason score  $\geq 8$ ) (D'Amico et al 1998)
2. Scheduled or planned radical prostatectomy and extended pelvic lymph node resection up to 6 weeks after the investigational PET/CT scan followed by histopathology assessment
3. ECOG performance status 0-2
4. Signed informed consent must be obtained prior to participation in the study
5. Participants must be adults  $\geq 18$  years of age

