#### Table 2-2Example 2 by 2 contingency table for each reader

		New 1	Reads
		Positive	Negative
Original	Positive	a	b
Reads	Negative	с	d

**Step 2:** Based on the contingency tables described above, a simple agreement rate, i.e.  $\frac{a+d}{a+b+c+d}$  and its corresponding 95% confidence interval (Agresti A, Coull BA 1998) will be estimated based on normal approximation.

Step 3: Finally, a Cohen's kappa statistic ( $\kappa_2$ ) and its corresponding 95% confidence interval will be estimated (Cohen J 1960; Cohen J 1968; Fleiss J, Levin B, Paik MC 2003) using the formula  $\kappa_2 \pm 1.96SE$ , where  $SE = \sqrt{\frac{p_0(1-p_0)}{N(1-p_e)^2}}$  (McHugh M 2012). Let N denote the number of re-reads (N = 20), k the number of categories (k = 2),  $n_{i1}$ the number of times the original reads were assigned to i (i = 1, ..., k) and  $n_{i2}$ the number of times the re-read were assigned to i (i = 1, ..., k). Then Cohen's kappa can be calculated as  $\kappa_2 = \frac{p_0 - p_e}{1-p_e}$ , where  $p_0$  is the relative agreements among the original and re-reads ( $p_0 = \frac{a+d}{a+b+c+d}$  in Table 2-2) and  $p_e = \sum_{i=1}^k \frac{n_{i1}}{N} \frac{n_{i2}}{N}$  ( $p_e = \frac{a+b}{N} \frac{a+c}{N} + \frac{c+d}{N} \frac{b+d}{N}$  in Table 2-2). Intra-reader variability will be calculated for the SAF.

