#### 5.4.2 Analysis supporting secondary objective(s)

For patient-level efficacy endpoints, their estimation and two-sided exact binomial 95% CIs will be calculated (implemented using SAS procedure FREQ with EXACT statement for one-way tables) (Clopper and Pearson 1934).

Only pelvic lymph node regions will be used to calculate region-level efficacy endpoints, and their estimation and two-sided exact binomial 95% CIs will also be calculated.

For inter- and intra-reader variability, 95% CIs will be calculated based on normal approximation with details given in Section 2.6.2.

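### The 95% CI for the inter-reader Fleiss kappa uses the standard error that holds only at kappa = 0; with two categories it is a constant that ignores the data

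*SAP*

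**What the plan says.** SAP 2.6.2 states that "scan inter-reader variability will be assessed by Fleiss' Kappa", computed on patient-level positive/negative calls. It sets n = 3 readings per participant and k = 2 categories, and defines N as the participants with an evaluable PET/CT. A "95% confidence interval will be estimated based on asymptotic estimation of the standard error"; the formula is printed, and the interval is kappa plus or minus 1.96 times that SE. The same section plans a raw summary beside it: "An additional table will be presented to show the distribution of agreements", giving the scans on which two and all three readers agree.

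For intra-reader agreement on 20 re-read scans, Step 2 is a raw rate ("Based on the contingency tables described above, a simple agreement rate") with its own interval. Step 3 is Cohen's kappa with a different SE, which depends on observed agreement.

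SAP 5.4.2 adds only this: "For inter- and intra-reader variability, 95% CIs will be calculated based on normal approximation with details given in Section 2.6.2". No bootstrap or other variance for the Fleiss kappa appears anywhere in either document.

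**The concern.** A confidence interval for kappa should become wider or narrower with the observed agreement and with the balance of positive and negative calls. The printed SE does neither. When there are two categories, the term that carries the category proportions vanishes and the rest cancels. What remains is the standard error for a true kappa of zero. The interval's centre moves with the data but its width cannot.

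Protocol 4.1 makes reader consistency a secondary endpoint because it bears on whether results carry over between institutions and on reliable diagnosis. If most scans are called positive, the SAP interval would overstate how precisely that consistency is known. High positivity is plausible. The trial enrols "Untreated high risk biopsy-proven PCa patients". Protocol 4.1 says "A patient will be judged as positive if at least one lesion in any region is visually positive". In the Phase I primary-staging patients (Protocol 1.1), "uptake corresponding to the pathology-proven cancer was shown in 4 of the 5 subjects".

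**Working it through.** **Inputs from the documents.** k = 2, n = 3, the SE formula and the ± 1.96 SE form (SAP 2.6.2). N is taken as 156 to 195: 156 evaluable participants as the minimum and 195 enrolled (SAP 1.1 and 3). These two figures reproduce. With 156 participants and a null sensitivity of 0.50, requiring at least 91 positives gives a one-sided alpha of 0.0225 and power of 0.9008 at 0.63, and 156/0.8 = 195. The SAP states no numeric SE or interval width for kappa.

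**Assumptions.** Positivity and true kappa are not in the documents, so ranges are used.

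**Step 1: the printed formula.** Write S = Σ p_j(1−p_j) and T = Σ p_j(1−p_j)(1−2p_j). The SAP formula is

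SE = sqrt(2) / [S × sqrt(N n (n−1))] × sqrt(S² − T).

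With two categories, p and q = 1 − p:

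- S = 2pq
- T = pq(1−2p) + pq(1−2q) = pq[2 − 2(p+q)] = 0
- so sqrt(S² − T) = S, which cancels, and SE = sqrt(2/(N n (n−1))) = sqrt(2/(6N)) = 1/sqrt(3N)

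At N = 156, SE = 1/sqrt(468) = 0.0462 and the half-width is 0.091. At N = 195, SE = 1/sqrt(585) = 0.0413 and the half-width is 0.081. Coding the formula as printed gives the same value for every p from 0.10 to 0.99.

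**Step 2: which standard error it is.** In simulation with true kappa = 0, the ratio between the actual SD of kappa and this SE is 0.96–1.01, and coverage is 95–96%. It is the null standard error.

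**Step 3: coverage away from zero.** Three binary reads per participant were simulated from a beta-binomial model with intraclass correlation equal to kappa, 40,000 data sets per cell. Coverage of the nominal 95% interval at N = 156:

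| Positive calls | kappa 0.6 | 0.7 | 0.8 | 0.9 |
|---|---|---|---|---|
| 63% | 92% | 95% | 98% | 99.7% |
| 80% | 85% | 88% | 94% | 99% |
| 90% | 70% | 74% | 83% | 93% |
| 95% | 54% | 58% | 66% | 77% |

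N = 195 is within about 1.5 points, except at 95%/0.9, where coverage is about 81–82%. Against the constant 0.046, the actual SD of kappa at N = 156 is 0.088 at 90%/0.6, 0.127 at 95%/0.6, 0.050 at 80%/0.8 and 0.030 at 63%/0.9. A second read model (common-correlation mixture) shows the same pattern; the two models together give 65–70% at 90%/0.6 and 61–66% at 95%/0.8.

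**Step 4: two hypothetical data sets, N = 156.**

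- Participants with 0/1/2/3 positive calls: 9/6/9/132. Mean agreement = (141 + 15/3)/156 = 0.936. Positive calls = 420/468 = 0.897. Chance agreement = 0.897² + 0.103² = 0.816. Kappa = (0.936 − 0.816)/(1 − 0.816) = 0.65. SAP interval 0.56–0.74; bootstrap 0.47–0.79.
- Counts 54/5/5/92. Mean agreement = (146 + 10/3)/156 = 0.957. Positive calls = 291/468 = 0.622. Chance agreement = 0.530. Kappa = 0.91. SAP interval 0.82–1.00; bootstrap 0.85–0.96.

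The SAP interval has the same width in both. It is too narrow in the first and too wide in the second.

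**Step 5: the intra-reader kappa (minor).** If all 20 re-reads agree and both categories occur, p0 = 1 and the Step 3 SE is 0, so the interval has no width. If a reader's 20 original reads are all positive, p0 = pe, and kappa is 0, or 0/0 when all re-reads are positive too. The chance of 20 positive originals is 0.80^20 = 1%, 0.90^20 = 12% or 0.95^20 = 36% per reader at those assumed positivities.

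**The case against.** The algebra is not in dispute; the case on the other side is about weight.

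- **Consequence.** Inter-reader kappa has no hypothesis, threshold or decision rule. Study success rests on exact binomial bounds for each reader and the two-of-three rule in SAP 2.5.2, which do not use this SE. The point estimate is right, and the planned agreement table shows raw agreement without it. All of this stands and limits the importance of the point.
- **Size is assumed.** The worst figures come from 95% positivity, which no document gives as an estimate. Four of five in Phase I has an exact 95% interval of about 28% to 99%. At 63% positivity, numerically the planning sensitivity, coverage is 92% or better; at 80% with kappa of at least 0.8 it is 94–99%. This stands as a caution about magnitude. However, planning sensitivity also requires anatomical correspondence with pathology, and counting a lesion in any region pushes reader positivity above it.
- **Model dependence.** The coverage figures assume exchangeable readers, and the second model moves some cells by about 5 points. The conclusion does not change.
- **The bootstrap is imperfect.** At 95% positivity and kappa 0.9 it covers only about 86–88% at N = 156 and 91% at N = 195. That is still better than the SAP interval's 77% and 81–82%. A non-null asymptotic SE would also serve and would keep the SAP's form.
- **Cohen's kappa.** Step 2 already reports the raw agreement rate, so only a fallback sentence is missing there.

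**Conclusion.** The concern holds. The interval is wrong as written, not merely under-described: for two categories the printed SE is the kappa = 0 value and depends only on N and the number of readers. That part needs no assumption.

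The direction and size of the error depend on positivity and kappa, which are unknown. Over the assumed grid at N = 156, the interval is near nominal at 63%/0.7 and 80%/0.8, clearly too narrow at 90–95% positivity with kappa 0.6–0.8 (54–83% coverage), and too wide at 63%/0.9 (99.7%). The effect is confined to the reported precision of one descriptive secondary endpoint. It should be corrected, but it does not threaten the study's main conclusions. The intra-reader gap is a minor addition.

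**What to change.** In SAP 2.6.2, replace the kappa ± 1.96 SE interval with a participant-level bootstrap percentile interval, resampling participants and keeping each one's three reads together. A jackknife or a variance valid at non-zero kappa would also do. Keep the printed SE only if a test of kappa = 0 is wanted. Change the normal-approximation sentence in SAP 5.4.2 to match, and show the new interval beside the agreement table already planned.

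In simulation at N = 156 the bootstrap covered 92–95% in 15 of the 16 cells above, the exception being 95%/0.9. The jackknife covered 91–95% in the same 15 cells and 87% in that one.

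For the intra-reader kappa, add a sentence: when kappa is undefined or its interval collapses, the Step 2 agreement rate is the reported result, with an interval that does not collapse at 20/20. The adjusted interval the SAP already cites gives 0.81–1.00 (upper limit truncated from about 1.03); the exact interval gives 0.83–1.00.

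The cost is SAP wording and a few lines of code, with no new reads. Intervals become wider when most scans are positive (average half-width about 0.17 instead of 0.09 at 90%/0.6, N = 156) and narrower when calls are balanced and kappa is high.
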